- **Describe the inclusion and exclusion criteria for this project:** This study will target adult patients who are planning to undergo photon or proton radiation therapy at UFHPTI for treatment of the breast or chest wall. As this type of treatment is rare in men, the study will focus on female patients only.
- **Provide a thorough step-by-step description of what you intend to do throughout the course of the study in a logical and sequential format:**

Hologram creation

For all patients included in this study, we will create holograms based on the external body contour derived from their planning CT dataset. This contour is routinely segmented during treatment planning; thus, we will only need to access the existing contour located in the software system MimVista and export it to our software system. We will also access patient setup photos located in a clinical file system and export these to our application.

Mixed-reality guided patient setup

At UFHPTI, we treat breast/chest wall patients using various modalities and techniques. In all cases, patient setup begins with a 3-point alignment. The additional use of IGRT depends on modality, approach, and patient-specific variables. Most patients treated with 3D conformal photon therapy (3DCRT) receive only weekly IGRT, including kV orthogonal and MV portal imaging. The 3-point alignment, thus, represents the standard setup for the majority of treatment, both here and across the nation, as 3DCRT is the most common technique for breast RT. As such, one of our primary aims is to pilot the clinical implementation of MixRT with the goal of accuracy similar to or better than a traditional breast setup involving 3-point alignment (5mm tolerance).

We will recruit 12 patients scheduled to receive whole breast or chest wall RT using a supine, 3DCRT or IMRT approach. All patients will be consented for a study comparing the accuracy of MixRT with a traditional 3-point alignment as quantified using CBCT. To control for setup variation which typically decreases after the first few treatment fractions, we will stratify patients into two groups using an alternating method. In the first group, the therapists will position the patient using 3-point alignment during fractions 1-5 (5 total), then using MixRT for fractions 6-10 (note:

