16 fractions is a common course of breast RT). For the second group, we will reverse the order, using MixRT for fractions 1-5 and 3-point alignment for fractions 6-10. In this way, each patient will serve as their own control. In all cases, patient alignment will be verified using CBCT which will be registered to the simulation CT by the treatment therapists using the standard clinical workflow. The magnitude of the resulting shift will be recorded. If further adjustment is necessary, the number of repeated CBCTs will be recorded along with the shift magnitude. All registrations will be reviewed by a board-certified radiation oncologist (one of the co-investigators) who will qualitatively assess the accuracy of the setup while blinded to the setup method. The process for mixed-reality alignment is noted below:

1. Identify the patient and initialize their hologram by detecting a QR-coded cube attached to the treatment device.
2. Setup the patient according to their setup photos, related immobilization devices (typically only an inclined breast board), and 3-point alignment. Further match the patient to their hologram as viewed through the HoloLens 2 device.
3. Utilize IGRT to verify proper alignment per protocol or departmental standards.
4. Make corrections as needed based on IGRT.
5. Repeat steps 1-3 if necessary.

For patients receiving proton therapy, setup typically includes routine CBCT, the challenges of which were previously discussed for non-rigid alignment including prolonged setup time and increased imaging dose. The primary goal of this sub-aim is thus to show that MixRT can reduce setup time and the amount of imaging dose in cases requiring CBCT alignment. To evaluate this, we will recruit an additional 12 patients scheduled to receive RT using a supine, pencil-beam scanning approach. As with 3DCRT/IMRT approach, we will divide patients into two groups using an alternating method and alternate the setup approach between fractions 1-5 and 6-10, reversing the order between the two groups. Setup time will be tracked from the moment the patient lies on the treatment couch to when the final position is confirmed by the therapist prior to treatment. Patient alignment will be verified/quantified in a similar manner as noted above.

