A window period of 2 additional fractions is permissible for the collection of study data. This window period is provided to allow a patient to remain on study through her 12th fraction of treatment if the patient is not able to receive the study intervention during one to two of her first 10 fractions.

To summarize, we intend to enroll 12 patients receiving either 3DCRT or IMRT and 12 patients receiving proton therapy. Within each modality, patients will be randomized into two groups using an alternating method. The order in which MixRT will be utilized will be reversed between the groups. The measured data will include registration accuracy (6 DoF shifts), setup time, and number of CBCT's utilized. Registration accuracy will be quantified using the image registration module that is used as part of the IGRT process. Setup time will be quantified using a stopwatch.

The number of CBCT's will be quantified via counting the number that are used during the setup process. Patients receiving photon IMRT receive daily CBCT as part of the standard of care. Thus, this investigation would likely not introduce additional imaging dose for these patients. For proton therapy CBCT is used weekly, and for 3DCRT it is not routinely used. Thus, this investigation would represent a marginal increase in the utilization of CBCT for these patients, up to 10 extra CBCT's nominally.

Setup during Verification CT

Radiotherapy patients at UFHPTI often receive repeat CT scans (verification scans) at periodic timepoints during the course of treatment to assess for anthropomorphic changes that could have dosimetric effect. Reproducing the posture from the initial CT simulation is critically important yet difficult to achieve due to the lack of real-time feedback. For patients who receive a verification CT (likely all proton patients), we will implement holographic alignment during this process and assess its accuracy in comparison to CT acquisition without the aid of holographic alignment. The procedure will be as follows:

1. Identify enrolled patients scheduled to receive a verification CT scan.
2. Setup patient without the aid of holographic alignment (standard method).
3. Acquire verification CT scan.
4. Dismantle the setup.
5. Utilize holographic alignment to correct patient posture. This involves a therapist wearing the HoloLens 2 device and viewing the patient's reference hologram overlaid the patient. The therapist will manually adjust the patient to match the hologram.

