- **Clearly state the nature of the experimental control (placebo, other treatment, historical) or the absence of a control:** Patients who receive verification CT, each patient will have their own control represented by the verification CT acquired without the use of holographic alignment. During the use of MixRT during patient setup, each patient will also have their own control represented by the sub-set of fractions where data is collected but holographic alignment is not employed.
- **Describe any randomization procedures:** Randomization is included during the use of MixRT guided patient setup where the patients are segmented into two groups. The order in which holographic alignment is introduced into the course of treatment is reversed for the two groups. The purpose is to control for setup variation which typically decreases after the first few fractions of treatment.
- **Describe completely all physical examinations, blood tests, x-rays, any special tests or procedures, surveys, questionnaires, and/or observations that will be used to obtain information about subjects:** No additional tests will be done that are outside the radiotherapy workflow. The study does include an increased utilization of specific aspects of the radiotherapy workflow, namely addition CT and CBCT acquisition.
- **Describe who will be responsible for obtaining the information and in what type of setting the information will be obtained:** Data will be collected during the course of radiotherapy treatment and during the acquisition of verification CT scans. Either the study investigators or trained radiation therapist will be responsible for collecting this data. The PI will serve as the primary data manager based on familiarity with the data.
- **Describe how these activities will answer the study questions:** The main question we seek to answer is whether mixed reality visualization is a feasible method for patient alignment in radiation therapy. To answer this question, we will collect relevant clinical data including registration error, registration time, and the amount of imaging used during the registration process. While we are not yet attaching power or a formal sample size structure to this data, we believe this data work together as our primary endpoints to answer the question of feasibility.

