- **Briefly outline the data analyses that are proposed and who will do the analysis:** Mean estimates and associated 95% confidence intervals will be attained for registration error and registration time for the mixed reality and standard of care methods and the paired difference of the two techniques. We will assess feasibility using a paired T-test. The hypothesis is that the mean paired differences across all measures of registration error and registration time are not significantly different than 3 mm and 5 minutes, respectively. The number of CBCTs collected as part of the registration process will be assessed subjectively since count data are not truly continuous. This analysis will be carried out by the study investigator and study statistician.
- **Describe your plan for conducting interim analysis. What stopping rules are in place?** N/A.

8.) Data Safety and Monitoring Plan:

- **Is there a Data Safety Monitoring Board (DSMB) or an oversight committee for this research project?** The UF Data Integrity & Safety Committee will provide oversight through annual monitoring.

- **Describe your plans for monitoring study conduct and subject safety:** The Principal Investigator will be responsible for monitoring.
- **Provide Information about the DSMB or committee including who is on the committee, how frequently will the committee meet, and when will you get information from the committee:** N/A

9.) Possible Discomforts and Risks:

- **Identify all discomforts and risks (physical, psychological, social, and/or economic) study participants may encounter, listing more common risks first and less common risks separately:** Based on prior study utilizing anthropomorphic phantoms, we anticipate that our patient alignment system will ultimately reduce setup time and the number of X-ray images used for alignment. We have yet to try this with patients, however, and there is a risk that it could marginally increase setup time, at least during the initial implementation.

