- **Discuss why the risks to subjects are reasonable in relation to the anticipated benefits and in relation to the importance of the knowledge that may reasonably be gained:** We believe the marginal increase in risk of developing a radiation induced malignancy incurred through participation in this study is low. The immediate benefit to the study participants is that the additional CT and CBCT may improve the accuracy of their setups for instances in which these images are acquired. The long-term benefit for patients outside the study cohort will be the knowledge gained about the clinical use of mixed-reality for patient setup. We believe this method can improve the patient setup and alignment process and will eventually make the process faster and with the use of less ionizing radiation.

10.) Possible Benefits:

- **Describe the potential benefits to subjects or to others that may be reasonably expected to result from the research:** Based on prior study utilizing anthropomorphic phantoms, we anticipate that our patient alignment system will ultimately reduce setup time and the number of X-ray images used for alignment. By reducing setup time, we increase patient comfort and minimize the risk of patient movement during treatment. By reducing the number of X-ray images used, we reduce the amount of ionizing radiation the patient receives.
- **If there is no potential for direct benefits, you must state this in the Informed Consent Form:** Due to the fact that CBCT will be utilized for all study fractions, patients may benefit from a more accurate setup if CBCT was not standard of care for their treatment approach.
- **Will the research study benefit future populations?** Yes, possibly.

11.) Conflict of Interest:

- **Describe any real or potential conflict of interest you or any other investigators may have with regard to this research project:** The principal investigator has filed a provisional patent application in coordination with UF Innovate related to concept of aligning a patient via hologram.
- **When deciding whether a conflict may exist, consider the following:**
 - **Do you, the University of Florida, or any of the sub-investigators hold a patent or license for any material, object, or process used in this project?** No
 - **Is a patent or license pending or under consideration or is there any intention to file a patent application at a later date?** Yes.

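### CBCT use is a joint primary endpoint and half of the proton sub-aim, yet the plan gives it a subjective assessment and no estimate or interval

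*Combined protocol and SAP*

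**What the plan says.** In section 6 (Research Plan), the answer on how the activities will address the study questions lists registration error, registration time and the amount of imaging, and says of the three: "we believe this data work together as our primary endpoints to answer the question of feasibility". Under mixed-reality guided patient setup, the proton cohort has its own aim: "The primary goal of this sub-aim is thus to show that MixRT can reduce setup time and the amount of imaging dose".

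The imaging data are collected objectively. The same section says that "The number of CBCT's will be quantified via counting the number that are used during the setup process", and that where further adjustment is needed, "the number of repeated CBCTs will be recorded along with the shift magnitude". The confidentiality answer in section 6 includes the number of CBCTs among the items held in the study spreadsheet. Section 10 (Possible Benefits) states that "CBCT will be utilized for all study fractions", so every study fraction has at least one.

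Section 7 promises means and 95% intervals, by method and for the paired difference, for registration error and registration time. On imaging it says only: "The number of CBCTs collected as part of the registration process will be assessed subjectively since count data are not truly continuous". It then adds: "This analysis will be carried out by the study investigator and study statistician". No summary statistic, interval or criterion for the CBCT count appears elsewhere.

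**The concern.** A primary endpoint that is counted at every study fraction is left to an undefined judgement. The stated reason, that counts are not continuous, does not prevent estimation: it bears on the choice of model, not on whether a mean, a difference and an interval can be calculated.

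No dose measurement is planned, so the CBCT count is the only recorded measure of the imaging half of the proton sub-aim. A subjective reading would leave that half without a quantitative answer. It would also commit the study to no repeat rate or SD for planning the larger comparative studies that the pilot is meant to support.

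The plan names the investigator and the statistician for the analysis as a whole. For the subjective judgement it gives no criterion, no specific assessor and no blinding. The only blinding described is for the radiation oncologist's review of registrations. A numerical summary fixed in advance removes the question.

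**Working it through.** The plan states no figure for CBCT use, so there is nothing to reproduce. The check is whether the planned data support an estimate with an interval, and how precise it would be.

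**Inputs from section 6.** 12 patients per cohort, allocated alternately to two orders (6 + 6); 5 fractions per method per patient, so 12 × 5 = 60 fractions per method. From section 7: 95% confidence (two-sided assumed). The SD of the paired difference and the repeat-CBCT rate are not given and are assumed below.

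**Estimator.** For each patient, take mean CBCTs per fraction with MixRT minus the mean with control. Average these differences within each order group, then average the two group means. A common period shift enters the two groups with opposite signs and cancels. This matches the protocol's own reason for reversing the order: "To control for setup variation which typically decreases after the first few treatment fractions".

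**Half-width.** t(0.975, 10 df) × SD × 0.5 × √(1/6 + 1/6) = 2.228 × SD / √12 = 0.643 × SD, where SD is pooled within order groups.

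| Assumed SD of paired difference | 95% half-width, CBCTs per fraction |
|---|---|
| 0.2 | 0.129 |
| 0.5 | 0.322 |
| 1.0 | 0.643 |

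**Does a t interval work on such counts?** A gamma-Poisson simulation (12 patients, 5 fractions per method, between-patient CV 0.5, 20,000 runs, plain paired t interval, more than one repeat per fraction allowed) gave coverage of 94.3% to 95.3% for control rates of 0.2 to 1.0 repeats per fraction.

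**What might the pilot show?** A second simulation used the period-adjusted estimator with binomial repeats (at most one per fraction) on the logit scale: patient SD 0.7, patient-by-method SD 0.7 on the within-patient difference, period shift 0.7 centred between periods, 20,000 runs. Rates are for a typical patient.

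| Repeat rate, control v MixRT | Interval wholly below 0 |
|---|---|
| 60% v 30% | 72% |
| 40% v 20% | 47% |
| 20% v 10% | 25% |
| 10% v 5% | 15% |

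For 40% v 20% the average result is about −0.18 ± 0.19. Without period adjustment the half-width rises from 0.19 to 0.21 and 47% falls to 40%. With equal rates of 30%, the interval excluded zero in 5.1% of runs, close to the nominal 5%.

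**The case against.** The strongest reply is that section 7 asks only for a brief outline, and that the word may mean descriptively, outside the t-test. The counts are stored, so a rate and SD could be computed at any time. The study calls itself an underpowered pilot, and no decision rule turns on the CBCT number.

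Part of this stands. The information is not lost; what is missing is a commitment to report it. The pilot label does excuse the absence of power and of a formal test. It does not excuse the absence of an estimate, because the same pilot gives estimates and intervals for the other two endpoints at the same sample size. The descriptive reading does not fit the plain word used, or the reason attached to it.

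A second objection is that the simulated percentages rest wholly on assumed inputs. That is right. For 40% v 20%, the 47% falls to about 40% if the 0.7 SD applies to each method independently, and rises to about 56% with no patient-by-method variation; a much larger SD of 1.4 brings it to about 25%. The percentages are illustrations, and the conclusion does not need them.

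A third is that period adjustment and a mixed model would give CBCT counts a fuller analysis than error and time receive. Period adjustment does apply equally to all three endpoints, and the mixed model is optional. Neither affects the need for an estimate. The 10 df hold only for 12 complete patients in a cohort.

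**Conclusion.** The concern holds. The plan adopts, for one of its three joint primary endpoints, a method whose stated reason is invalid and which yields no estimate or interval. This is a stated choice, not a missing detail. The data to be collected support a paired difference with a 95% half-width of 0.643 times the SD of that difference, or 0.13 to 0.64 CBCTs per fraction for assumed SDs of 0.2 to 1.0. Coverage was close to nominal under the assumed rates. The interval may well include zero even if repeats are halved. That is acceptable in a pilot, provided the result is presented as estimation. The finding itself rests only on the text and on the fact that the interval can be computed; the size rests on assumed SDs and repeat rates. It should be corrected; the feasibility conclusion on imaging depends on it, but participant safety does not.

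**What to change.** Replace the CBCT sentence in section 7 with text along these lines:

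*For each cohort, CBCTs per fraction will be summarised by method: the distribution, the mean number of repeats beyond the first, and the proportion of fractions with any repeat. The within-patient difference, MixRT minus control, will be given with a 95% confidence interval, adjusted for period by averaging the mean differences of the two order groups (pooled SD; 10 degrees of freedom with 12 complete patients). A Poisson or binomial mixed model with method and period will be a sensitivity analysis.*

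Repeats beyond the first are the informative part, since each study fraction has at least one CBCT. If the number of patients with both methods differs from 12, the degrees of freedom become that number minus 2. No power claim or significance test is needed.

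The cost is a short replacement passage in the analysis section, a few lines of code and slightly more analysis work. It needs no extra patients, visits or scans. The downside is that a wide interval may have to be reported.

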The study also involves an increased utilization of CT and CBCT in order to quantify the difference in registration accuracy when using the mixed-reality method. Patients who receive a verification CT will receive 1-2 additional CT scans. During MixRT guided patient setup, patients will receive at least 0-10 additional CBCT scans (depends on modality). While it is routine for breast 3DCRT to employ planar kV imaging weekly as opposed to CBCT, it is not uncommon to utilize daily CBCT for difficult cases. Daily CBCT is also used for all cases where an IMRT approach is utilized. The dose from CBCT imaging is orders of magnitude less than the dose received during treatment, (approx. 1-2 mGy vs 45 Gy). According to the linear-no threshold model, there is non-zero risk of developing a radiation induced malignancy from any level of ionizing radiation. We believe the marginal increase in risk incurred through participation in this study, however, is low based on the limited amount of radiation delivered during CT and CBCT acquisition and the fact that these patients are already receiving high levels of ionizing radiation as part of their cancer treatment.

Only those Adverse Events related to the use of the HoloLens will be reported.

- **Identify potential financial risks study participants may incur:** None
- **Indicate any procedures, medications, tests, or therapies that study participants (or their insurer) will have to pay for. Are these considered standard therapies or are they specific to the research study?** None
- **Describe procedures to protect against or minimize potential discomforts and risks:** For individual cases, we will discontinue the use of the holographic alignment system if setup time is increased by more 30% during two consecutive sessions.

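### The 5-minute time criterion has no stated direction and is met by a non-significant t-test, and patients stopped under the 30% rule do not enter the feasibility conclusion

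*Combined protocol and SAP*

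**What the plan says.** - **Section 7, data analyses:** "We will assess feasibility using a paired T-test". The hypothesis is that mean paired differences in "registration error and registration time are not significantly different than 3 mm and 5 minutes, respectively". Means with 95% confidence intervals are planned for each method and for the paired difference. The 5 minutes has no sign and no stated role.
- **Section 9, minimizing risks:** for individual patients, "we will discontinue the use of the holographic alignment system if setup time is increased by more 30% during two consecutive sessions". The time against which the increase is measured is not given.
- **Section 7, interim analysis:** the item "Describe your plan for conducting interim analysis. What stopping rules are in place" is answered as not applicable. That item concerns interim looks, so it does not contradict Section 9. However, nothing else in Section 7 mentions discontinued patients.
- **Section 6:** of registration error, registration time and imaging, "we believe this data work together as our primary endpoints to answer the question of feasibility". Each patient's control is "the sub-set of fractions where data is collected but holographic alignment is not employed". One group has standard setup first. "For the second group, we will reverse the order, using MixRT for fractions 1-5", with standard setup in fractions 6-10.
- **Section 9, risks:** with the new system, "there is a risk that it could marginally increase setup time, at least during the initial implementation".

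**The concern.** Three gaps meet in one feasibility decision.

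First, the criterion is met by failing to reject a difference of 5 minutes. Failing to reject is not evidence that a time cost is acceptable. If 5 minutes is a tolerated slowdown, a method that costs no time should fail the test and one that costs the full 5 minutes should pass it.

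Second, on that same reading the 30% rule can take patients off MixRT at slowdowns smaller than the one the test accepts.

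Third, stopped patients are not counted anywhere in the analysis, so a feasible result would not show how many there were.

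Feasibility is the pilot's main question. Its data are meant to frame larger studies and eventual regulatory clearance (Section 5).

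**Working it through.** The plan gives no power, standard deviation or site setup time, so there is no figure of its own to reproduce.

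**1. Where the two criteria meet (slowdown reading).** Inputs: 5 minutes (Section 7) and 30% (Section 9). Break-even standard setup = 5 / 0.30 = 16.7 min. Below that, the 30% line lies under 5 minutes. The only setup times in the document are 11 and 6 min, from a study cited in Section 4 (Surface-Guided Radiotherapy), not from this site:
- at 11 min: 0.30 x 11 = 3.3 min, and 5/11 = 45%;
- at 6 min: 0.30 x 6 = 1.8 min, and 5/6 = 83%;
- at 20 min the order reverses: 0.30 x 20 = 6.0 min.

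**2. Who the rule can reach.** MixRT-first patients have no standard study fractions of their own during fractions 1-5. If the 30% is measured against a patient's own study fractions, only the 6 standard-first patients of 12 can be stopped. If it is measured against a fixed departmental mean, all 12 can. Both were run.

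**3. Simulation.** All of the following is assumed:
- cohorts of 12; 5 standard and 5 MixRT fractions; lognormal times; standard mean 11 min;
- between-patient CV 20%; SD of the MixRT effect 1-3 min; fraction CV 20-40%;
- registration time means setup time, and sessions means MixRT fractions;
- a patient stops when two consecutive MixRT times exceed 1.3 x the reference; MixRT times up to then are kept, and later fractions count as standard setup;
- two-sided 5% paired t-test against 5 min.

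The literal test passes in about 94-95% of cohorts at a true +5 min and in 0-14% at a true 0. The first figure is simply 1 - 0.05 and owes nothing to the 30% rule. The observed mean must exceed about +6.3 to +8.2 min (6.3/11 = 57%, 8.2/11 = 75%) before the test calls MixRT slower than 5.

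| True difference | Passes literal test and more than half of reachable patients stopped | Upper 95% limit below 5 min |
|---|---|---|
| 0 | at most 4% | 86-100% |
| +2 min | at most about 13% | 42-99% |
| +4 min | about 41-55% | 7-28% |
| +5 min | about 55-85% | 1-3% |

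At +5 min, 61-77% of reachable patients are stopped with the own-mean reference. That is 0.61 x 6/12 = 31% to 0.77 x 6/12 = 39% of the cohort. With the fixed reference it is 59-72% of all 12.

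**4. Sensitivity.** With the looser count of at least half of reachable patients stopped, the joint result at +5 min is 78-93% at an 11 min baseline, 31-54% at 20 min and 18-43% at 25 min. A second model (normal times, all patients reachable, true baseline as reference, SDs of 1-3 min) gives 92-95% for more than half stopped at 11 min and +5, and at most 17% at 20 min. The size therefore depends heavily on the unknown baseline and on the model.

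**5. Is a confidence limit enough?** No. At an assumed 6 min baseline and true +3 min, the upper limit lies below 5 with more than half of reachable patients stopped in about 12-88% of cohorts.

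**6. Saving reading.** With a true -5 min tested against -5, 0-4% of patients are stopped and the joint event does not occur.

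**The case against.** The strongest reply is that 5 minutes may well be a saving. The proton sub-aim is to shorten setup, Sections 6, 9 and 10 expect faster alignment, and the cited 11 and 6 min differ by exactly 5. The only increase foreseen is a marginal one. This reading is at least as well supported as a tolerated slowdown, and it removes the conflict.

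Further, the 30% rule is a safeguard for individuals and the t-test concerns a group mean. An individual limit tighter than a group criterion can coexist with it. The planned means and intervals would show a 5-minute slowdown to an attentive reader, and the protocol admits that the pilot is underpowered.

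Most of this stands, and it rules out three stronger readings that a reader might infer:
- **That the two criteria contradict each other outright.** The text fixes neither the sign of the 5 minutes nor the site's setup time.
- **That most of the cohort would be stopped.** With an own-fraction reference at most half can be, and a large share is stopped only if the true slowdown is near or above 30%.
- **That the 94-95% pass rate comes from the 30% rule.** It comes from accepting a null hypothesis.

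The reply does not repair the decision rule. If 5 minutes is a saving, non-significance still rewards noisy data, and a clearly larger saving would fail. Nor does it supply a count of stopped patients.

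**Conclusion.** The concern holds in limited form. As written, time feasibility rests on a non-significant test against a figure without a direction, and discontinuations under Section 9 play no part in the conclusion. On the slowdown reading the rule gives the wrong answer at both ends. It can also return a feasible result with more than half of the reachable patients stopped: often when the true slowdown is 4-5 minutes, seldom at 2. On the saving reading only the unsound inference and the missing count remain.

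The break-even of 16.7 min is exact. Every simulated percentage rests on an assumed baseline and assumed variability, and the joint figures also on the assumed 30% reference. The amendment should be made, but this is not a demonstrated contradiction between the two sections.

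**What to change.** 1. **Wording.** State the direction and role of the 5 minutes. Reconcile Sections 6, 7 and 9 on what the 30% is measured against in MixRT-first patients. The values are for the study team; no threshold is proposed here, and the two criteria need not share a scale.
2. **Decision rule.** Replace non-significance with a confidence-limit criterion: the relevant 95% limit of the paired time difference must lie on the favourable side of the team's value.
3. **Stopped patients.** Report the number stopped over the number the rule could reach, with an exact 95% interval, as part of the feasibility conclusion.
4. **Data.** Keep MixRT times recorded before stopping. In the simulations at +5 min this moves the estimated mean by +0.1 to +0.8 min against MixRT.

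**Cost:** protocol and analysis wording plus one tabulated count, with no new visits or data. The confidence-limit criterion is harder to meet: about 42% of cohorts pass at a true +2 min in the noisiest setting. The stop proportion will be imprecise: 8/12 gives 34.9-90.1%, and 4/6 gives 22.3-95.7%.
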